## Imaging Cohort

If subject is in the Imaging Group (See **Appendix VI and Imaging Guidance Document** for further details):

- Post-procedure angiography, IVUS and OCT are required based on respective imaging groups.
- If post-dilatation was performed, post-procedure imaging must be conducted following last balloon inflation.

If two target lesions are treated, post-procedure imaging must be done on the first target lesion after its successful treatment, and then after successful treatment of the 2nd target lesion.

### 7.3.5 *Bailout Stenting or Alternative Procedures*

Bailout procedures may be performed if the subject experiences:

- Dissection requiring intervention
- Occlusive complication as evidenced by a decrease in target vessel flow
- Chest pain or ischemic changes measured by ECG that do not respond to repeat balloon inflations, medical therapy or lytic agents
- Unplanned additional device is required to cover the target lesion

In the randomized subjects, if a bailout device is required for a target lesion (e.g., for edge dissection), the same device as the implanted device must be used. Overlap of the bailout stent/scaffold with the implanted stent/scaffold should be 1-2 mm. Gaps should be avoided.

- o Use Absorb BVS if target lesion is treated with Absorb BVS.
- o Use XIENCE if target lesion is treated with XIENCE.
- o If a bailout with an Absorb BVS device cannot be delivered to the site of the lesion, the device should be carefully withdrawn and a XIENCE used.
- o If an appropriate size Absorb BVS is not available XIENCE can be used.

If during the Lead-In phase a bailout is required, the investigator should use an appropriately sized XIENCE stent and not an Absorb BVS.

The Imaging Cohort subjects that receive metallic stent bailout of an Absorb BVS treated lesion will be required to complete imaging follow-up at the protocol specified time points of 3 years for IVUS or OCT, depending on which imaging group the subject is in. However, the subject's imaging data will not be included in the imaging study analysis and will not be counted towards the associated powered secondary endpoints analysis. These subjects may be replaced by another subject that received an Absorb BVS without metallic stent overlap.

**IMPORTANT:** It is required that the bailout device be placed so that there is no visible gap between the Absorb BVS and the bailout device. In such a case, at least 1 mm (minimum) to 2 mm (maximum) overlap is required.

**IMPORTANT:** In the rare event of acute occlusion following Absorb BVS placement, the bailout device should be XIENCE and deployed within the Absorb BVS such that the Absorb BVS is completely covered by the bailout device if this is believed to be in the best interest of the patient.

Although a bailout procedure is not considered a major adverse cardiac event (MACE) unless the subject sustains death, emergent CABG, PCI or MI, such procedures should be avoided unless required for safe subject management.

### **7.3.6 Final (Post-procedure) Angiography**

Angiographic imaging will also be performed after the Absorb BVS or XIENCE stent deployment. Physicians should follow accepted hospital imaging practice to ensure good apposition of the Absorb BVS or XIENCE to the vessel wall. For angiographic imaging, post-implantation images should be captured the same orthogonal views that were used for the pre-procedure images. Intracoronary nitroglycerine should be re-administered before final angiography.

### **7.3.7 Final (Post-procedure) IVUS and OCT**

For subjects not required to have post-procedure imaging, IVUS and OCT may be performed post-procedure if the investigator believes there is incomplete apposition of the device. The procedure will be performed according to the site's standard. However, if malapposition is seen and post-dilatation required, a non-compliant balloon should be used and in the case of Absorb BVS, do not dilate the Absorb BVS beyond the dilatation limit which is 0.5 mm above the nominal diameter. Repeat angiography in orthogonal views must be performed after any additional inflations.

### **7.3.8 Imaging Assessment**

Subjects from the Imaging Cohort will receive angiography (includes vasomotion assessment), IVUS and OCT at pre-specified time-points (**Section 7.5**). Imaging assessments should be conducted per core lab guidelines in the Imaging Guidance Document distributed to each site. Intracoronary nitroglycerine should be given before all imaging runs to avoid spasm and afford maximal luminal dimensions.

Any Imaging Cohort subject that did not receive the assigned Absorb BVS or XIENCE stent will not receive follow-up imaging procedures. These subjects will be clinically followed under the study. If an Imaging Cohort subject had a TLR prior to the imaging follow-up, the imaging data at the time of TLR and at the protocol specified later imaging time points will be analyzed but not included in the imaging endpoint analysis. If an Imaging Cohort subject had a TVR or angiogram prior to the imaging follow-up, the subject will continue to have the protocol specified imaging follow-up and will not be replaced. If an Imaging Cohort subject has two target lesions but only one target lesion was successfully treated with the assigned device, the unsuccessfully treated target lesion must be imaged post-treatment and at the specified follow-up

times only if the assigned study device was implanted for lesion treatment. Imaging Cohort subjects that receive metallic stent bailout of an Absorb BVS treated lesion will be required to complete imaging follow-up at the protocol specified time points of 3 years for IVUS or OCT, depending on which imaging group the subject is in. However, the subject's imaging data will not be included in the imaging study analysis and will not be counted the associated powered secondary endpoints. These subjects may be replaced by another subject that received an Absorb BVS without metallic stent overlap.

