#### ***5.2 Powered Secondary Endpoint(s)***

##### **Imaging Cohort Powered Secondary Endpoints**

Imaging Cohort Powered Secondary Endpoints are based on the pooled subjects from the Imaging Cohort of Absorb III (~ 200 angiographic subjects and ~150 IVUS subjects) and subjects from the Absorb Japan RCT (~ 400 angiographic subjects, and ~150 IVUS subjects).

One of the key attributes that differentiates Absorb BVS from metallic stents is the progressive mechanical weakening of the scaffold with polymer degradation over time, which allowed for vessel movement and gradual outward remodeling (positive) to accommodate any increases in the in-scaffold intimal hyperplasia that may limit blood flow. In both the Absorb Cohort A and Cohort B trials, Absorb BVS treated vessels have shown evidence of vessel movement and late lumen and scaffold enlargement, providing anatomic indication that the vessel can adapt and enable the natural Glagov process.

The vasomotion endpoint assesses the ability of the in-scaffold segment to move when the vessel is no longer mechanically constrained. Angiography will be used for the vasomotion assessment. The assessment of late lumen enlargement will be evaluated by the in-stent/scaffold mean lumen area change ( $\Delta$ MLA) from post-procedure to 3 years by IVUS.

1. The in-stent/scaffold mean lumen area change, from post-procedure to 3 years by IVUS (mean lumen area measured after nitrate infusions, superiority test, ~300 pooled subjects).
2. The in-stent/scaffold mean lumen diameter change, between pre- and post-nitrate infusion at 3 years by angiography (superiority test, ~600 pooled subjects).

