### **5.3 Additional Secondary Endpoint(s)**

In ABSORB III the following clinical secondary endpoints will be analyzed. Secondary imaging endpoints will be analyzed in the Imaging Cohort.

- **Acute Success:** (Combined Clinical/Angiographic Endpoint)
  - Device success (Lesion level analysis)
  - Procedural success (Subject level analysis)
- **Clinical Endpoint** in hospital and at each follow-up point (30 days; 180 days; 1, 2, 3, 4 and 5 years).
  - **Component**
    - Death (Cardiac, Vascular, Non-cardiovascular)
    - Myocardial Infarction
      - Attributable to target vessel (TV-MI)
      - Not attributable to target vessel (NTV-MI)
    - Target Lesion Revascularization (TLR)
      - Ischemia driven TLR (ID-TLR)
      - Non ID TLR (NID-TLR)
    - Target Vessel Revascularization (TVR,
      - ID TVR
      - Non ID TVR
    - All coronary revascularization
  - **Composite Endpoints**
    - Death/All MI
    - Cardiac Death/All MI
    - Cardiac Death/TV-MI/ID-TLR (TLF)

- Cardiac Death/All MI/ID-TLR (MACE)
- Cardiac Death/All MI/ID-TLR/ID-TVR, non TL (Target Vessel Failure, TVF)
- Death/All MI/All revascularization
- **Scaffold-Thrombosis / Stent Thrombosis (per ARC definition)**
  - Timing (acute, sub-acute, late and very late)
  - Evidence (Definite and Probable)
- **Imaging Endpoints:**

Imaging endpoints will be analyzed on Imaging Cohort subjects only.

○ **Angiography:**

All angiographic endpoints will be collected post-procedure and at 3 years

- In-segment late loss (LL)
- In-device LL
- Proximal LL (proximal defined as 5 mm of tissue proximal to the device placement)
- Distal LL (distal defined as 5 mm of tissue distal to the device placement)
- In-device/in-segment/proximal/distal minimum lumen diameter
- In-device/in-segment/proximal/distal %Diameter Stenosis (DS)
- In-device/in-segment/proximal/distal angiographic binary restenosis
- In-device net gain (change in minimum lumen diameter between 3 years and post-procedure)
- The magnitude of in-stent/scaffold mean lumen diameter change (absolute value) at 3-years follow-up from pre-nitrate to post-nitrate
- The normalized in-stent/scaffold mean lumen diameter change at 3-years follow-up from pre-nitrate to post-nitrate, defined as,

$$\frac{\text{In - Stent/Scaffold Mean Lumen Diameter change}}{(\text{Proximal Mean Lumen Diameter change} + \text{Distal Mean Lumen Diameter change})/2} \times 100\%$$

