### 7.3.8.4 Vasomotion Assessment

- At the 3-year follow-up, assessment of vessel movement in response to nitroglycerin infusion will be conducted. Please see the Imaging Guidance Document for the details of this assessment.
- Vasomotion assessment should not be assessed under the following conditions, and those subjects may be replaced for the imaging analysis:

- Target lesion treated with Absorb BVS with metallic stent overlap
- Target lesion undergoing other PCI procedures prior to 3-year imaging follow-up
- If target lesion has  $\geq 50\%$  stenosis at the time of the 3-year assessment and does not clearly require revascularization, FFR should be conducted to determine if lesion is flow limiting. If the lesion is flow limiting and requires revascularization, vasomotion assessment should not be done.
- Details regarding the angiographic assessment of the vessel and timing of nitroglycerine infusion are further detailed in the Imaging Guidance Document.

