#### **Imaging Cohort Powered Secondary Endpoint 1**

The in-stent/scaffold mean lumen area change ( $\Delta$ MLA) from post-procedure to 3 years by IVUS (mean lumen area is to be measured after nitrate infusions) will be evaluated using the difference between the two means of the two treatment arms in the pooled subjects from the Imaging Cohort of ABSORB III and ABSORB Japan. Superiority testing will be performed with a two-sided alpha of 0.05. The null ( $H_0$ ) and alternative ( $H_A$ ) hypotheses for the superiority test are:

$$H_0: \Delta\text{MLA}_{\text{Absorb}} - \Delta\text{MLA}_{\text{XIENCE}} = 0$$

$$H_A: \Delta\text{MLA}_{\text{Absorb}} - \Delta\text{MLA}_{\text{XIENCE}} \neq 0.$$

$\Delta\text{MLA}_{\text{Absorb}}$  and  $\Delta\text{MLA}_{\text{XIENCE}}$  are the in-stent/scaffold mean lumen area changes in the Absorb BVS and XIENCE arms, respectively.

The sample size calculation is based on the following assumptions:

- The in-stent/scaffold mean lumen area change at 3 years for the Absorb BVS arm is assumed to be  $0.5 \pm 1.69 \text{ mm}^2$
- The in-stent/scaffold mean lumen area change at 3 years for the XIENCE arm is assumed to be  $-0.4 \pm 1.17 \text{ mm}^2$
- Two-sided alpha= 0.05
- $\sim 150$  subjects from the Imaging Cohort in ABSORB III, 50% IVUS follow-up rate at 3 years

- ~150 subjects from ABSORB Japan, 70% IVUS follow-up rate at 3 years
- ~15% of all subjects will have dual target lesion treatment.

An effective sample size of 207 lesions (138 for the Absorb BVS arm and 69 for the XIENCE arm) will provide approximately 99.4% power using two sample t-test.

The sample size calculation was performed using NCSS PASS 2008 (Hintze JL, 2002. PASS User's Guide-II. NCSS).

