#### **10.4.2 Powered Secondary Endpoint Analyses**

Analysis of the Powered Secondary Endpoints for angina, for all revascularization, for ID-TVR, and for diabetic indication will include subjects from the primary analysis group. Pearson's Chi-square test will be used for superiority testing based on the ITT and PTE populations for the powered secondary endpoint for angina. Fisher's exact test will be used for superiority testing based on the ITT and PTE populations for the powered secondary endpoints for all revascularization and for ID-TVR. Analysis of the Imaging Cohort Secondary Endpoints 1 and 2 will include pooled subjects from the Imaging Cohort of ABSORB III and ABSORB Japan. Two sample t-test will be used for superiority testing based on the ITT and PTE populations.

Details of the analyses for the powered secondary endpoints can be found in the statistical analysis plan (SAP).

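### Images taken at TLR are kept out of every ABSORB III imaging endpoint, so restenosis and late loss are understated and the IVUS lumen-area comparison needs a sensitivity analysis

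*Combined protocol and SAP*

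**What the plan says.** The rule is in Section 7.3.8 of the ABSORB III protocol. It begins "If an Imaging Cohort subject had a TLR prior to the imaging follow-up, the imaging data at the time of TLR" and continues, for that image and for "the protocol specified later imaging time points will be analyzed but not included in the imaging endpoint analysis". The images are therefore read, but none counts towards an endpoint. The next sentence of the section keeps subjects who had a TVR or an angiogram in imaging follow-up, so the exclusion is specific to re-treatment of the target lesion.

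The endpoints affected are these:

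- Section 5.3 lists "In-device/in-segment/proximal/distal angiographic binary restenosis" together with late loss, minimum lumen diameter (MLD) and percent diameter stenosis (%DS). All are assessed in the Imaging Cohort only. Section 10.4.3 makes them descriptive.
- Section 5.2 defines powered imaging endpoint 1 as "The in-stent/scaffold mean lumen area change, from post-procedure to 3 years by IVUS", pooled with ABSORB Japan. Section 10.3.2 adds "Superiority testing will be performed with a two-sided alpha of 0.05".
- Section 7.3.8.4 separately bars the vasomotion test (powered endpoint 2) for "Target lesion undergoing other PCI procedures prior to 3-year imaging follow-up".

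On analysis, Section 10.4.2 states "Two sample t-test will be used for superiority testing based on the ITT and PTE populations" without mentioning the TLR exclusion. Section 10.4.10 uses available data and names sensitivity analyses only for the TLF primary endpoint. The detailed SAP text for the imaging endpoints, to which Section 10.4.2 refers, is not in the document reviewed.

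**The concern.** Leaving out an image taken after a TLR is sensible, because it shows a re-treated lesion. The image at the TLR is different. It is the last view of the lesion as treated with the randomised device, and it tends to show the narrowest lumens. Binary restenosis is defined in Appendix II as %DS of at least 50%, and a lesion re-treated for restenosis is an event that this endpoint is meant to count. Under the rule it leaves both numerator and denominator. Late loss, MLD and %DS lose the same lesions.

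The exclusion happens after randomization and depends on the outcome, so it sits badly with an analysis described as ITT. For powered endpoint 1, intended to support a label claim on late lumen enlargement, the same selection could shift the between-arm difference if TLR rates differ.

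The rule is also worded per subject. In a subject with two target lesions it could remove the lesion that was never re-treated.

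**Working it through.** **Plan's own figure first.** Section 10.3.2 assumes 150 ABSORB III subjects with "subjects from the Imaging Cohort in ABSORB III, 50% IVUS follow-up rate at 3 years", that is 75 subjects. It also assumes 150 ABSORB Japan subjects at 70%, that is 105, and about 15% dual-lesion treatment. Effective lesions = (75 + 105) × 1.15 = 207, split 138:69. With means +0.5 and -0.4 mm², SDs 1.69 and 1.17, and an unequal-variance two-sample t-test at two-sided 0.05, power is 99.36% against 99.4% stated. The figure reproduces. Excluding 4.5%, 6% or 10% of the 207 lesions leaves 99.1%, 99.1% or 98.8%, so the issue is selection and not lost power.

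**Binary restenosis.** Let t be the proportion with TLR before imaging, r the restenosis rate in the other lesions, and q the proportion of TLR lesions with %DS of at least 50%.

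- Rate as the plan would report it: r.
- Rate over all lesions: tq + (1 - t)r.
- Understatement: t(q - r). It is positive whenever TLR lesions are restenotic more often than the rest, and it grows with t.

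The documents give no 3-year TLR rate for this trial. Section 2.1.9 reports ischemia-driven TLR in ABSORB Cohort B of 6.0% at 2 years, and 4.5% at 3 years in Group 1. Assume t = 4-8%, r = 3-5% and q = 1 (the upper bound):

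- t = 4%, r = 3%: 0.04 + 0.96 × 0.03 = 6.9%
- t = 6%, r = 3%: 0.06 + 0.94 × 0.03 = 8.8%
- t = 8%, r = 5%: 0.08 + 0.92 × 0.05 = 12.6%

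The endpoint would read 3-5% against at most about 7-13%. The arm comparison is affected too. With r = 2% in both arms and TLR of 6% against 3%, the all-lesion rates are 7.9% and 4.9%, while the rule reports 2% in each.

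**Powered endpoint 1.** Take the plan's means as those of lesions without TLR, and let L be the lumen area change at TLR. Excluding TLR lesions inflates the Absorb-minus-XIENCE difference by

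B = tA(0.5 - L) - tX(-0.4 - L).

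No document gives L or TLR by arm. With L assumed at -3 and -4 mm²:

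- Absorb 6%, XIENCE 3%: 0.210 - 0.078 = 0.132, and 0.270 - 0.108 = 0.162
- Absorb 8%, XIENCE 4%: 0.280 - 0.104 = 0.176, and 0.360 - 0.144 = 0.216
- Equal rates t: B = 0.9t, so 0.036 at 4% and 0.072 at 8%, whatever L is
- Absorb 1.8%, XIENCE 4.1% (the example 1-year ID-TVR rates in Section 10.3.2, used only as a proxy): 0.063 - 0.107 = -0.044, and 0.081 - 0.148 = -0.067

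The rule is documented only for ABSORB III, which supplies 75/180 = 42% of expected IVUS subjects. If ABSORB Japan has no such rule, multiply by 0.417. The 2:1 imbalance then gives 0.055 to 0.090 mm², equal rates 0.015 to 0.030, and the reversed case -0.018 to -0.028, all against a planned difference of 0.90. In lesion counts, ABSORB III contributes 75 × 1.15 = 86, split about 57:29, so TLR of 6% against 3% is about 4 lesions.

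**The case against.** The strongest objections concern powered endpoint 1, and most of them stand.

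- **Direction.** A reader might infer that Absorb would look better on a label-claim endpoint because more of its lesions failed. The documents do not support that. Section 10.3.1 assumes the same TLF rate, 7.0%, in both arms, and the ID-TVR example in Section 10.3.2 favours Absorb, which turns the sign negative.
- **Size.** A loss of 3-4 mm² is 46-61% of the post-procedure mean lumen area of 6.53 mm² in Cohort B (Table 2.3). The endpoint averages over the device, whereas TLR may follow a focal narrowing or one in the 5 mm margins. With L = -1 and 6% against 3%, B is 0.090 - 0.018 = 0.07 before allowing for pooling.
- **Estimand.** The endpoint is lumen change at 3 years, and lumen area changes over time in Cohort B (6.36 mm² at 6 months, 6.85 at 2 years). A value from an early TLR measures something else. IVUS is required only post-procedure and at 3 years (Section 7.3.8.2), so it may not exist at TLR. Missing follow-up, assumed at 50% in ABSORB III, is a much larger loss than TLR.

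On restenosis, a reader might take 7-13% as the true rate, because TLR implies restenosis. It does not. Appendix II sets no %DS threshold for TLR, and ischemia-driven TLR can rest on a functional study alone. Nor do the endpoints describe only lesions that did well: restenosis without TLR, or first found at the 3-year angiogram, is not removed by this sentence. TLR is also reported separately at every visit, so failures are not hidden.

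What remains is that restenosis, late loss, MLD and %DS as written omit lesions already re-treated for restenosis. Nothing visible in the plan counts them, carries their value forward or tests the effect of leaving them out.

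**Conclusion.** The point holds. For the descriptive angiographic endpoints the exclusion is selection on the outcome. It understates restenosis and late loss in both arms, and more in the arm with more TLR. The illustration, 3-5% reported against at most about 7-13%, rests on assumed TLR of 4-8% and on every TLR lesion being restenotic.

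For powered endpoint 1 the exclusion can favour whichever arm has more TLR, but neither direction nor size can be settled from the documents. The effect is close to zero with equal rates. It is about 0.06-0.09 mm² of 0.90 if Absorb has twice the TLR, TLR lesions lost 3-4 mm² and ABSORB Japan has no such rule. It has the opposite sign if XIENCE has clearly more TLR. This justifies a sensitivity analysis and not a change to the main test.

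The TLF primary endpoint and the definition of study success are untouched. The missing SAP detail is a real limit: a suitable analysis may exist there, in which case it needs reconciling with Section 7.3.8.

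**What to change.** - In Section 7.3.8, exclude only images taken after the TLR, and state that this applies per lesion and not per subject.
- For binary restenosis, late loss, MLD and %DS, use the last angiogram before re-intervention as the follow-up value for that lesion.
- Keep the 3-year analysis of powered endpoint 1 as planned. Add a sensitivity analysis that includes TLR lesions, using IVUS at TLR where it was recorded and otherwise ranking the lesion worst.
- Report the number of lesions excluded because of TLR, by arm.
- Leave the vasomotion exclusion in Section 7.3.8.4 as it is.
- Reconcile Section 7.3.8 with the ITT statement in Section 10.4.2 and with the SAP, and state which TLR rule ABSORB Japan uses.

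The cost is wording in the protocol and SAP. No new procedure is needed, since Section 7.3.8 already has the images at TLR read. The drawbacks are less favourable restenosis and late-loss figures, and a shorter follow-up time for the few TLR lesions.

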### 7.3.8.1 QCA of Target Vessel

- QCA will be performed pre-procedure, post-procedure and at the 3-year follow-up for the imaging study subjects.
- Angiography must be performed per the angiographic core laboratory guidelines.

### 7.3.8.2 IVUS Pull-back of Target Vessel

- IVUS pullback (20 MHz or 40-45 MHz catheter can be used) is required post-procedure and at 3-year follow-up for the imaging study subjects.
- Pullback of the IVUS catheter should be performed from the distal reference to the guiding catheter, per IVUS core laboratory guidelines.
- If IVUS reveals any findings such that additional PCI is performed, an additional IVUS run must be performed after the last intervention.
- **Caution:** It is important to place the IVUS transducer in the center of the lumen to avoid lifting or disturbing the device struts during pullback.

